### **Study Timeline**

Recruitment is projected to begin in October 2019 and extend through approximately May 2020. Results are projected to be available for hypotheses 1-5 by September 2020, and for Hypothesis 6, by May 2021.

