### **Study Aims and Hypotheses**

The goals of the study will be as follows:

- 1. To examine the perceived acceptability, usefulness, and client satisfaction following participation in the Single-Session Consultation (SSC) service at the Krasner Psychological Center (KPC) and Mind Body Clinical Research Center (MBCRC) among waitlisted adolescent and adult clients
- 2. To examine therapists' perceived acceptability, feasibility, and effectiveness of the single session consultation at three time points: pre-training, post-training, and post-SCC administration
- 3. To assess the demand for and feasibility of providing the SSC service at the Krasner Psychological Center and Mind Body Clinical Research Center (i.e., documenting the proportion of clients who choose to participate in the service when it is offered; documenting the number of sessions successfully completed, rescheduled, and/or cancelled).
- 4. To assess whether levels of proximal clinical outcomes (e,g, hope, agency) are improved immediately following completion of the SSC, both in adolescent and adult clients.
- 5. To assess whether levels of psychological symptoms are improved two weeks following completion of the SSC, both in adolescent and adult clients.
- 6. To assess rates of (a) remaining on the clinic waitlist for therapy and (b) length of subsequent treatment at the Mind Body Clinical Research Center and Krasner Psychological Center among individuals participating in the SSC, relative to clients who sought out services in the six months prior to the SSC being offered to clients (January June 2019).

Hypotheses associated with each of these aims will be as follows:

- 1. Clients' proximal clinical outcomes (e,g, hope, measured by the Beck Hopelessness Scale 4 item version, and Agency, measured by the State Hope Scale; both primary study outcomes), which are hypothesized to serve as mechanisms for intervention effects, will improve from immediately pre-SSC completion to immediately post-SSC.
- 2. Adolescent and adult clients will perceive the SSC at the Mind Body Clinical Research Center and Krasner Psychological Center as acceptable and useful in addressing their clinical needs, indexed by mean ratings of at least 3.5 out of 5 across the five items on the "Consultation Feedback Form".

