- 3. The SSC will show feasibility as a model for service provision at the Mind Body Clinical Research Center and Krasner Psychological Center (i.e., a majority [>50%] of clients who are offered the SSC service will elect to receive it, and most [>75%] of clients who schedule an SSC appointment will attend)
- 4. Clients' overall psychological symptom levels will reduce two weeks after the SSC, relative to symptoms immediately prior to the SSC

- 5. No prediction is made about therapists' perceived acceptability, feasibility, and effectiveness of single session interventions at baseline or their subsequent assessment, given the novelty of research in this domain.
- 6. Clients who receive the SSC will be less likely to remain on the clinic wait list—and, among those who elect to remain on the clinic wait list, total therapy duration will be briefer—relative to clients who sought service at the Mind Body Clinical Research Center and Krasner Psychological Center prior to the SSC service being offered.

Note that data will be available for testing hypotheses 1-5 substantially sooner than for testing hypothesis 6, as the duration of clients' potential future psychotherapy at the Krasner Psychological Center and Mind Body Clinical Research Center is impossible to determine. Whereas data for the first four hypotheses will be available two weeks subsequent to recruitment completion, data for the fifth hypothesis may be unavailable for up to a year subsequent to recruitment completion. Accordingly, the authors may report results from hypotheses 1-5 in a manuscript or conference presentation prior to completion of data collection for hypothesis 6, noting that data relevant to hypothesis 6 will be reported at a to-be-determined future date. Data relevant to hypothesis 6 (which requires extraction of aggregate client information associated with previous Mind Body Clinical Research Center and Krasner Psychological Center clients) will not be collected, and thus will remain unknown to investigators, until all relevant data are available for analysis (i.e., until all clients who completed the SSC and chose to receive full-length psychotherapy have terminated their course of treatment at the clinic).

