To address our fifth research question (for which no hypotheses are proposed), we will aggregate descriptive statistics from the "Therapist Beliefs about SSC" scales and will compare the scales between (1) pre-training and post-training and (2) post-training and post-SSC administration. Positive perceptions of the SSC at any given time-point will be defined by a mean rating of at least 3.5 out of 5 across all items; less-than-positive perceptions will be defined by a mean rating of less than 3.5 out of 5 across all Likert scale-rated items. We will report all qualitative data collected via this measure—specifically, we will report therapists' written responses to openended questions about their perceptions of the SSC. Because the scope and amount of this qualitative data are likely to be limited, and given the exploratory nature of the present study, we do not intend to conduct any formal qualitative data analyses in this study.

To address Hypothesis 6, we will conduct two 2-tailed independent-samples t tests. First, we will assess whether the percentage of individuals removing themselves from the clinic's waitlist after completing the SSC differs from the percentage of individual who had removed themselves from the waitlist in the six months prior to the SSC's being offered at the clinic. A difference with a p value of < .05, with a higher value for the SSC group, would suggest that individuals who receive the SSC may be more likely to voluntarily remove themselves from the clinic waitlist than individuals who had not received the SSC in the past. Second, we will calculate the mean number of psychotherapy sessions completed at the Mind Body Research Clinical Center and Krasner Psychological Center among individuals who receive the SSC and elect to remain on the clinic's waitlist. We will then test whether this mean number of sessions differs from the mean

number of sessions completed by clients who began psychotherapy in the six months prior to the SSC's being offered at the clinic. A difference with a p value of < .05, with a lower value for the SSC group, would suggest that individuals who receive the SSC may be more likely to have a shorter course of psychotherapy than those who do not receive the SSC prior to full-length treatment. Note that for both of our Hypothesis 6 analyses, we will restrict our sample of previously-seen clients to those in the same age-range as in the study sample, in order to optimize comparability between groups.

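### The historical comparator for Hypothesis 6 is not consistently defined: its dated window fits the six-month rule only under an unstated launch date, and three different events define who belongs to it

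*SAP*

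**What the plan says.** The historical group for Hypothesis 6 is described in four places in the SAP.

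- **Study Aims and Hypotheses, Aim 6:** "clients who sought out services in the six months prior to the SSC being offered to clients (January June 2019". This is the only place that gives calendar dates.
- **Study Aims and Hypotheses, Hypothesis 6:** clients who sought service "prior to the SSC service being offered", with no window.
- **Analytic Plan, first Hypothesis 6 test:** the percentage of people who "had removed themselves from the waitlist in the six months prior to the SSC's being offered at the clinic", set against the percentage of SSC clients who leave the list after their session. No dates.
- **Analytic Plan, second Hypothesis 6 test:** the mean "number of sessions completed by clients who began psychotherapy in the six months prior to the SSC's being offered at the clinic", set against the mean for SSC clients who choose to stay on the waitlist. No dates.

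For both tests, "we will conduct two 2-tailed independent-samples t tests". The one step towards comparability is age: "we will restrict our sample of previously-seen clients to those in the same age-range as in the study sample".

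The Study Timeline gives the SAP's only start date: "Recruitment is projected to begin in October 2019 and extend through approximately May 2020". No separate date is given for the first offer of the service.

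**The concern.** Hypothesis 6 is the only part of the plan that compares SSC clients with another group of clients, and the comparison is not randomised. Both results therefore depend on which earlier clients are extracted and from what point they are followed. Two things are unsettled.

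First, the dated window ends in June 2019, while the only start date in the SAP is October 2019. The rule and the dates describe the same cohort only if something happened in July 2019 that the SAP does not mention.

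Second, the event that places a client in the historical group changes from one passage to the next. People who sought services, people who left the waitlist and people who began therapy in a given half-year are different sets. The SSC side of each test is defined differently again. A difference in removal rate or session count could then arise from the way the groups were assembled and not from the SSC.

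**Working it through.** No sample-size or power formula applies. The check is calendar arithmetic followed by a side-by-side reading.

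**Inputs**

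- Dated window: January to June 2019 (Aim 6).
- Rule: the six months before the SSC was offered (Aim 6, and both tests in the Analytic Plan).
- Recruitment: October 2019 to about May 2020, projected (Study Timeline).
- Date of first offer: not given.

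**Step 1: can the dated window be reproduced from the rule?**

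- Assume the first offer coincides with the start of recruitment. October 2019 minus six months gives April to September 2019. The overlap with January to June 2019 is April, May and June, that is 3 of 6 months. The dated window is not reproduced.
- Work backwards from the dated window. If June 2019 is the last month before the offer, the first offer falls in July 2019. The dated window is reproduced, and July to September 2019 (3 months) lies between the comparator and the start of recruitment without explanation.

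**Step 2: calendar months against recruitment.** Recruitment covers October to May, 8 calendar months.

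| Window | Months shared with October to May | Recruitment months without a counterpart | Window months outside recruitment season |
|---|---|---|---|
| January to June (dated) | January to May: 5 of 6 | October to December: 3 of 8 | June: 1 of 6 |
| April to September (rule, if first offer is October) | April, May: 2 of 6 | October to March: 6 of 8 | June to September: 4 of 6 |
| October 2018 to May 2019 (same months, one year earlier) | 8 of 8 | none | none |

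**Step 3: the defining events.**

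| Place | Historical group | SSC group |
|---|---|---|
| Aim 6 | Sought services in the window | Took part in the SSC |
| First test | Left the waitlist in the window | Left the waitlist after the SSC |
| Second test | Began psychotherapy in the window | Received the SSC and chose to stay on the waitlist |

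In the first test the historical wording counts departures within a window. It does not say who forms the denominator, and some of those who left may have joined before the window opened. The SSC clock starts at the session and has no stated end, so the two percentages cover different periods at risk.

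In the second test the historical group contains only people who started therapy. The SSC group is defined by staying on the list, so it may include people who never start. The SAP does not say how they are counted. If they enter with zero sessions, they lower the SSC mean, which is the hypothesised direction, and have no counterpart in the historical group.

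Step 3 does not depend on the launch date.

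**The case against.** The strongest reply is that the Study Timeline dates recruitment to the study, not the first offer of the service, and only as a projection. The section on sample size already speaks of recruitment as ongoing, so the timeline wording may simply be out of date. Aim 6 gives explicit dates, and the natural reading of the Analytic Plan is that its undated phrase refers back to them. The April to September window appears nowhere in the SAP. This stands. A reader might infer that the passages flatly contradict each other, but the documents do not support that, because a July 2019 launch would reconcile them.

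A reader might also infer that the comparator comes from a different season. For the dated window that is largely wrong, since 5 of its 6 months fall in the recruitment season. No six-month window could cover all eight recruitment months, and the SAP gives no figures on seasonal variation.

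Nor does sharing 3 of 6 months mean that up to half of the historical clients would change. That would need monthly intake counts, which the SAP does not give.

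Finally, one might infer that the analyst could choose a window after seeing the data. The SAP says that the historical data stay uncollected and unknown until all relevant data are available. This does not remove every choice at extraction, but it limits the risk.

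Hypothesis 6 is also not primary: hope and agency are. Its results are reported later and its conclusions are worded cautiously. That limits how much weight the point should carry.

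None of these replies answers the mismatch of defining events, which holds under any launch date.

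**Conclusion.** The point holds in two parts of unequal strength.

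The window is conditionally inconsistent. If the SSC was first offered in October 2019, the rule and the stated dates share 3 of 6 months. If it was first offered in July 2019, they agree. The SAP neither states nor excludes either date, and the October date is a projection.

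The entry events are inconsistent without any condition. Seeking services, leaving the waitlist and beginning psychotherapy define different historical groups, no common follow-up is set for waitlist removal, and the session-count test applies different inclusion rules to its two groups.

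Season is a secondary matter. Under the stated window, October to December have no counterpart and June lies outside the recruitment season. The size of any resulting bias cannot be derived from the SAP.

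This is a low-cost improvement worth making. No primary outcome, sample size or alpha figure is affected.

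**What to change.** Make the change before the historical data are extracted, which the SAP places after SSC clients have finished therapy.

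1. State one calendar-dated window, in identical terms, in Aim 6 and in both Hypothesis 6 analyses.
2. Define both groups by the same entry event, joining the waitlist.
3. For waitlist removal, apply the same length of follow-up to both groups, with everyone who joined in the window as the historical denominator.
4. For session counts, apply the same inclusion rule to both groups: either only those who begin therapy, or all who stay on the list, with non-starters handled alike.
5. Choose the window. Taking the same calendar months as actual SSC enrolment one year earlier (October 2018 to May 2019 if the projected dates hold) would also remove the partial seasonal mismatch. If January to June 2019 is kept, state when the SSC was first offered and correct the six-month wording where it does not hold.

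The cost is a slightly different extraction query and some SAP wording. A common entry event will not make the groups fully comparable: SSC clients must still be on the list when they attend their session, and that should be reported as a limitation.
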